7.4.1 Pregnancy

At the time a Principal Investigator or delegated staff becomes aware that a study participant became pregnant following study participation, the Principal Investigator or Study Coordinator will report the pregnancy immediately by phone and/or by faxing a completed Pregnancy Report to [REDACTED] within one working day of being notified of the pregnancy report.

The report will include the following elements:

- Participant (mother's) coded study identifier;
- Date of participant's last menstrual period;
- Total accumulated dose of study treatment administered to date;
- Date of study medication administration

The investigator will follow the subject until completion of the pregnancy and must assess the outcome in the shortest possible time but not more than 30 days within completion of the pregnancy.

Upon delivery, miscarriage or abortion, the Principal Investigator or Study Coordinator must forward a follow-up Pregnancy Report with any relevant information on the present condition of the fetus to [REDACTED], including:

- Mother's coded study identifier(s);
- Gestational age at delivery, miscarriage or abortion;
- Birth weight, gender, length and head circumference, if available;
- Apgar scores recorded after birth, if available;
- Any abnormalities.

If the outcome of the pregnancy **meets the criteria for immediate classification of an SAE** (e.g., spontaneous or therapeutic abortion [any congenital anomaly detected in an aborted fetus is to be documented], stillbirth, neonatal death, or congenital anomaly), the investigator will report the event by phone and by faxing a completed SAE report form to [REDACTED] within one working day of being notified of the pregnancy report.

If the trial is completed before the outcome of the pregnancy is known, [REDACTED] will assume the responsibility for following up on the pregnancy. [REDACTED] will contact the Investigator or Study coordinator on or around the potential expected date of delivery to follow-up on the outcome of pregnancy and will also check on the status of the infant 8 weeks post-delivery. Upon awareness of the pregnancy outcome and known status of the infant following 8 weeks of delivery, the investigator will complete the applicable pregnancy report forms and fax to [REDACTED] within 1 day of being notified.

7.5 Post Study Adverse Events

7.5.1 Non-serious Adverse Events

Adverse events that are identified at the last assessment visit (or the early termination visit) must be recorded on the AE eCRF with the status of the AE noted.

7.5.2 Serious Adverse Events

Serious adverse events that are identified on the last assessment visit (or the early termination visit) must be recorded on the AE eCRF page and reported to Perrigo according to the procedures outlined above. Subjects with unresolved previously reported serious adverse events, or any new serious adverse events identified on the last assessment visit, should be followed by the investigator until the events are resolved, or the subject is lost to follow-up. Resolution means the subject has returned to the baseline state of health, or the investigator does not expect any further improvement or worsening of the adverse event. The investigator should continue to report any significant follow-up information to Perrigo up to the point that the event has resolved. Any serious adverse event reported by the subject to the investigator that occurs after the last assessment, and are determined by the investigator to be reasonably associated with the use of the study drug, should be reported to Perrigo.

8. STATISTICAL ANALYSIS

The sections that follow highlight sample size determination and the planned analyses for this study. A statistical analysis plan (SAP) will be prepared separately from this protocol which gives descriptions of the statistical methods, models, hypotheses and subject populations to be analyzed. The SAP will be completed and approved before locking the database and unblinding the study and will serve as a companion to the protocol and the *de facto* documentation of the proposed statistical evaluation. The SAP will be completed and finalized prior to breaking the blind.

8.1 Statistical Analysis Plan

8.1.1 Analysis Populations

The following populations are defined for the purpose of analyses:

- Intent-to-Treat (ITT) (safety population): Any subject that was randomized and received and used study medication.

Protocol No: PRG-NY-15-002

- Modified Intent-to-Treat (mITT): Any subject that was randomized, met eligibility criteria, received and used study medication, and that has at least one post-baseline efficacy assessment.

- Per Protocol (PP): Any subject:
 - Who met eligibility criteria
 - Who was randomized and received and used study medication
 - Who applied the study medication on Days 1-2 [REDACTED]
 - Who completed Visit 4/Day 57 (End of Study/Early Termination Visit) within window OR was discontinued from the study [REDACTED].
 - Without significant protocol violations that could have interfered with the administration of the treatment or the precise evaluation of treatment efficacy

[REDACTED]

[REDACTED]

[REDACTED]

[REDACTED]

[REDACTED]

[REDACTED]

[REDACTED]

8.1.2 Planned Analysis

All subjects who received study medication will be evaluated for safety. The efficacy analysis will be conducted on both the PP and the mITT subject populations. Two-sided hypothesis testing will be conducted for tests. Resulting p-values less than 0.05 will be considered statistically significant. No adjustments of p-values for multiple comparisons will be made. No interim analyses are planned. SAS software will be used for all data analyses and tabulations.

The treatment response will be summarized by treatment group for the end-of-study evaluation. The primary efficacy endpoints will be the proportion of subjects with clinical response of success defined as complete clearance (absence) of all clinically visible Actinic Keratosis lesions identified at the Baseline visit and no new Actinic Keratosis lesions in the treatment area at Visit 4/Day 57.

[REDACTED]

[REDACTED]

[REDACTED].

8.1.3 Sample Size Considerations

[REDACTED]

[REDACTED]

[REDACTED]

8.1.4 Efficacy Measures and Analysis

Clinical endpoints

The primary efficacy measure will be the proportion of subjects with clinical response of success defined as complete clearance (absence) of all clinically visible Actinic Keratosis lesions identified at the baseline visit and no new Actinic Keratosis lesions in the treatment area at Visit 4/Day 57.

Equivalent efficacy

For the proportion of subjects with clinical success, the Test treatment will be considered to be therapeutically equivalent to the Reference treatment if the 90% confidence interval on the difference between Test and the Reference proportions is contained within the interval -20% to +20%. The confidence interval will be constructed using Wald's method with Yates' continuity correction.

[REDACTED]

Superiority

Superiority will be demonstrated if both the active treatments (Test and Reference) are shown to be superior to the vehicle.

The proportion of subjects with clinical success for each active treatment will be compared to that of the Vehicle using a Z-test with Yates' continuity correction.

All hypothesis tests will be two-sided at a significance level of $\alpha = 0.05$, except confidence intervals which will be based on $\alpha = 0.10$ (i.e. 90% coverage).

[REDACTED]

[REDACTED]

8.1.5 Safety and Adverse Events Analysis

The frequency and percent of subjects with adverse events will be summarized by MedDRA (Version 15.1) system organ class and preferred term and by severity and relationship to study drug for all three treatment groups. The adverse events reported by at least five percent of the subjects in any treatment group will also be tabulated. The comparable safety of the Test and Reference treatments will be evaluated by statistical comparison of the proportion of subjects who reported any adverse events. The test and reference treatments' frequency and distribution of application site reactions of erythema, flaking/scaling, crusting, swelling, vesiculation/postulation, and erosion/ulceration will be summarized and compared descriptively. Safety comparisons will be performed only for the safety intent-to-treat population.

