	
examine the subject to establish the clinical diagnosis of Actinic Keratosis (defined as the presence of 4 to 8 clinically typical, visible, discrete, nonhyperkeratotic, nonhypertrophic Actinic Keratosis lesions) contained within a contiguous 25cm² area on the trunk or extremities (“treatment area”)
 
The number of Actinic Keratosis lesions in the selected treatment area will be counted (and a total provided) and recorded at Visit 1/ Day 1 (Baseline) and at Visit 4/Day 57 (should any exist) on source documentation and eCRFs. Additionally, new lesions not present at the baseline visit will also be counted and recorded on source documentation and eCRFs at Visit 4 or an Unscheduled Visit if applicable.
 
At Visit 4/Day 57, the principal investigator or sub-Investigator will visually inspect the treatment area for any lesions and will confirm complete clearance of Actinic Keratosis lesion in the eCRF if lesion count is equal to zero at Visit 4/Day 57. Complete clearance is defined as the absence of clinically visible Actinic Keratosis lesions identified at Visit 1 or new lesions since Visit 1.
 
At the baseline visit (prior to initial dosing) and each subsequent visit, application site reactions of erythema, flaking/scaling, crusting, swelling, vesiculation/pustulation, and erosion/ulceration will be recorded on the source document and eCRF.

Endpoints:
	
The primary efficacy endpoint will be the proportion of subjects with clinical success defined as complete clearance (absence) of all clinically visible Actinic Keratosis lesions identified at the baseline visit and no new Actinic Keratosis lesions in the treatment area at Visit 4/Day 57.

Safety:
	
The incidence of all adverse events reported during the study will be summarized by treatment group. Equivalence of the test and reference with regard to safety will be evaluated by comparing the nature, severity and frequency of their adverse event profiles. In addition, the test and reference treatments’ frequency and distribution of application site reactions of erythema, flaking/scaling, crusting, swelling, vesiculation/pustulation, and erosion/ulceration will be summarized and compared descriptively.

ABBREVIATIONS

AE	Adverse Event
AK	Actinic Keratosis
ANOVA	Analysis of Variance
ATC	Anatomic Therapeutic Chemical (classification of drugs)
eCRF	Electronic Case Report Form
EDC	Electronic Data Capture
FDA	US Food and Drug Administration
GCP	Good Clinical Practice

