2.2 Safety

Safety of the test and reference products will be compared by evaluating the nature, severity and frequency of their adverse event profiles. All adverse events that occur during the study (from the moment a subject signs an informed consent/assent) will be recorded. Descriptions of reactions or complaints will include the approximate date of onset, the date the adverse event ended, the severity of the adverse event, and the outcome. Comparisons between the treatment groups will be made by tabulating the frequency of subjects with one or more adverse events (classified into MedDRA terms) during the study. Pearson's Chi-Square test or Fisher's Exact test, whichever is most appropriate, will be used to compare the proportion of subjects in the two active treatment groups with any adverse event. [REDACTED]

Protocol No: PRG-NY-15-002

of the subject's adverse events (AEs). At this visit, the Follow-Up Telephone Call/Day15, Visit 3/Day 29 and Visit 4/Day 57 will be scheduled.

A Follow-Up Telephone Call will be made by study staff to the subject at Day 15 to review and assess subject compliance (diary completion), record AEs, update concomitant medication use, and to remind the subjects of the protocol requirements and next study visit schedule.

At Visit 3/Day 29 (Interim) and Visit 4/Day 57 (End of Study), subjects will be asked if they experienced any adverse events, taken any concomitant medications and generally complied with protocol requirements. The diary dispensed at Visit 2 will be collected and reviewed with the subject, and a new diary will be dispensed at Visit 3/Day 29. The diary dispensed at Visit 3 will be collected and reviewed at Visit 4/Day 57. Safety will be assessed by the monitoring of all adverse events (AEs) and clinically significant changes from Visit 1/Day 1 (Baseline) and an application site reaction assessment will be conducted at Visit 3/Day 29 and Visit 4/Day 57.

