To compare the safety and efficacy profiles of Perrigo New York, Inc.'s Ingenol Mebutate Topical Gel 0.05% to Picato® Topical Gel 0.05% (Ingenol Mebutate Topical Gel 0.05%) and to demonstrate the superior efficacy of the two active formulations over that of the vehicle in the treatment of Actinic Keratosis.

3 Study Design

For the purpose of exploring the above objectives, the study will be conducted as a double-blind, randomized, parallel-group, vehicle-controlled, multicenter trial.

Each subject will be randomly assigned to one of following treatment groups :

- (1) Test: Ingenol Mebutate Topical Gel 0.05%, Perrigo New York, Inc.
- (2) Reference: Picato® Topical Gel 0.05% (Ingenol Mebutate Topical Gel 0.05%), Leo Pharma Inc.
- (3) Vehicle of test product, Perrigo New York, Inc.

Subjects will be admitted into the study only after written informed consent has been obtained and all of the inclusion and none of the exclusion criteria have been met. Randomization will be performed according to a computer generated randomization scheme where the treatment group designation has been assigned to the subject number. The treatment designation will remain blinded until the final database is closed. An independent third party will generate and hold the randomization code throughout the study. Randomized subjects will apply assigned

topical gel [redacted] once daily for two (2) consecutive days to the selected treatment area (one contiguous skin area of approximately 25cm² treatment area on the trunk/extremities) avoiding contact with the eyes, mouth and other body areas during and after gel application.

Subjects will be scheduled for an office visit for Visit 1/Day 1 (Baseline), Visit 2/Day 3 (±1 days) (Post-Treatment Interim), Visit 3/Day 29 (±3 days) (Interim), and Visit 4/Day 57 (±2 days) (End of Study). Safety will be assessed by monitoring adverse events at each visit and during a Follow-Up Phone Call/Day 15 (±3 days).

4 Populations To Be Analyzed

Three subject populations are defined as follows:

- (1) An intent-to-treat (ITT) subject is any individual who: (a) was randomized into the study, and (b) received and applied at least one dose of study medication;
- (2) A modified intent-to-treat (mITT) subject is any individual who: (a) was randomized into the study, (b) met eligibility criteria, (c) received and applied at least one dose of study medication, and (d) had at least one post-baseline efficacy assessment;

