5.6 Safety Variables and Analyses

Duration of Treatment and Medication Compliance

Number of applications, days of exposure, and compliance rate will be summarized by treatment group using descriptive statistics. For each subject, the overall duration of treatment (days) will be calculated using the following formula:

$$\text{(Date of last application of study medication)} - \text{(Date of first application of study medication)} + 1.$$

Medication compliance rate (%) will be calculated for each subject as follows:

$$\text{(Total number of applications used)} / \text{(Expected number of applications)} * 100\%.$$

Subjects who complete the study are expected to have 2 applications. [REDACTED]

[REDACTED] For prematurely discontinued subjects, expected number of applications will be determined based on the

overall duration of treatment by the time of discontinuation. Descriptive summaries of exposure and medication compliance rate will be provided by treatment group for the ITT subjects

Adverse Events

Adverse events (AEs) will be coded in MedDRA, version 15.1. Treatment-Emergent Adverse Event (TEAE) is defined as any AE occurs on or after applying the first dose of study drug. Number and percent of subjects reporting TEAEs will be tabulated by treatment group. Summaries will be presented by body system and preferred term for the ITT population, and further by severity and relationship to study medication. TEAEs reported by 5% or more subjects for any treatment group will also be summarized. In the summaries of incidence rates (frequencies and percentages), severity and relationship to study drug, subjects who report more than one event that are mapped to the same preferred term will be counted only once under the strongest severity and relationship, accordingly Fisher's exact test will be used to compare the proportions of subjects of the two active treatment groups who report any TEAE.

Treatment-Emergent Serious Adverse Events (TESAEs) will be discussed within the clinical study report. TESAEs and TEAEs that led to treatment interruption or discontinuation will be presented in data listings.

Concomitant Medications

Concomitant medications will be coded using the WHO Drug Dictionary, version September 2014, and will be presented in data listings.

Application Site Reactions

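### Comparable safety of Test and Reference is to be judged by a statistical comparison, but the only readable methods are tests of no difference, with no interval for the difference

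*Protocol*

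**What the plan says.** Three places in the protocol set out the safety comparison of the two active arms.

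- Synopsis, Safety: "Equivalence of the test and reference with regard to safety will be evaluated by comparing the nature, severity and frequency" of their adverse event profiles.
- Section 2.2 names two tests, Fisher's exact and Pearson's chi-square, and leaves the choice open: "whichever is most appropriate, will be used to compare the proportion of subjects in the two active treatment groups with any adverse event". The text directly after this sentence is redacted.
- Section 8.1.5: "The comparable safety of the Test and Reference treatments will be evaluated by statistical comparison of the proportion of subjects" who reported any adverse event. The same section also plans tabulations by system organ class, preferred term, severity and relationship, and a descriptive comparison of six application site reactions.

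The SAP's objective is worded more neutrally: "To compare the safety and efficacy profiles of Perrigo New York" and so on. In SAP 5.6 the method is Fisher's "exact test will be used to compare the proportions of subjects of the two active treatment groups who report any TEAE", in the ITT population. Protocol 8.1.2 and SAP 5.1 make testing two-sided with a 0.05 threshold.

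For efficacy the plan proceeds differently. Under Protocol 8.1.4, Test is equivalent to Reference "if the 90% confidence interval on the difference between Test and the Reference proportions is contained within the interval -20% to +20" per cent, and SAP 5.5 writes non-equivalence as the null hypothesis.

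**The concern.** Section 8.1.5 names an aim, comparable safety, and a means, a statistical comparison of one proportion. The means that can be read take no difference as the null hypothesis. Such a test can give evidence that the arms differ, but failing to reject does not give evidence that they are alike. The smaller or noisier the trial, the more easily it fails to reject.

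The efficacy section shows that the plan has the right tool: an estimated difference with a confidence interval. For safety, the only readable inferential result will be a p-value, and a p-value does not show how large an excess on Test the data still allow. For a generic compared with its reference product, that is the question a safety reader will ask.

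**Working it through.** There is no plan figure to reproduce: Protocol 8.1.3 (sample size) and the allocation ratio in 6.2.4 are redacted, and no adverse event rate is readable. What follows illustrates the size under assumed inputs.

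**Inputs.** From the documents: two-sided test at 0.05, Fisher's exact test (SAP 5.6), and the Wald interval with Yates' correction (the efficacy method in Protocol 8.1.4 and SAP 5.5). Assumed: equal active arms of n = 100, 150 or 200, and a 20% Reference rate of subjects with any event.

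**Step 1. How often a true excess is non-significant.** The probability is one minus the sum, over all pairs of counts at which Fisher gives p < 0.05, of Bin(x; n, p_T) × Bin(y; n, p_R).

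| n per arm | Fisher power, 30% vs 20% | Non-significant | Fisher power, 40% vs 20% | Non-significant |
|---|---|---|---|---|
| 100 | 0.313 | 69% | 0.844 | 16% |
| 150 | 0.469 | 53% | 0.960 | 4% |
| 200 | 0.597 | 40% | 0.991 | 1% |

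The weakness is therefore in moderate excesses. At these sizes a 20-point excess would usually be detected.

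**Step 2. What a p-value leaves unsaid.** Interval: d ± [z × √(p_T(1−p_T)/n + p_R(1−p_R)/n) + 1/n].

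Take 33/100 on Test and 20/100 on Reference, the largest Test count at n = 100 that Fisher still calls non-significant (p = 0.054):

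- d = 0.33 − 0.20 = 0.13
- standard error = √(0.33×0.67/100 + 0.20×0.80/100) = √0.003811 = 0.0617
- 95% half-width = 1.96 × 0.0617 + 0.01 = 0.131
- 95% interval = −0.1 to +26.1 points

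At n = 150, 45 against 30 gives p = 0.062. Here d = 0.10, the standard error is √(0.37/150) = 0.0497, and the half-width is 1.96 × 0.0497 + 0.0067 = 0.104, so the 95% interval is −0.4 to +20.4 points. At n = 200, 57 against 40 gives p = 0.062 and −0.4 to +17.4 points.

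In each case the interval agrees with Fisher in including zero. What it adds is the upper limit.

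**Step 3. Which interval to report.** The efficacy analysis uses 90%. In the same three cases the 90% Wald-Yates lower limits are +1.8, +1.2 and +1.0 points, so a 90% interval would exclude zero while Fisher is non-significant. A 95% interval has the same level as the 0.05 test and avoids that conflict here. Agreement is not guaranteed in every table or with every interval method, which is one reason to present the interval as an estimate rather than a second test.

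**The case against.** The strongest reply is that the plan never makes the faulty inference. Neither document says that p of 0.05 or more will be read as comparable, so the percentages in Step 1 measure the risk of a reading that the plan does not state. This stands. A reader might infer that the sponsor will declare safety equivalence from a non-significant Fisher test, but the documents do not support that. The synopsis word equivalence is attached to a comparison of the nature, severity and frequency of adverse events, which is a descriptive exercise and not the test. Only the sentence in 8.1.5 ties a comparability aim to a statistical comparison.

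It is also true that text after the test sentence in Protocol 2.2 is redacted, so an interval or reading rule there cannot be excluded. Event counts by arm are tabulated, so a reader could compute an interval. The illustration depends wholly on assumed sizes and rates.

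A reader might further infer that the two documents conflict over which events are tested. Protocol 2.2 records events "from the moment a subject signs an informed consent/assent", while a TEAE in the SAP "is defined as any AE occurs on or after applying the first dose of study drug". But the consent phrase governs recording and does not define the tested set, and Protocol section 8 makes the SAP the working statement of the statistical evaluation. This is mostly a refinement, and one word in the comparison sentences settles it.

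What survives is narrower: 8.1.5 promises an evaluation of comparable safety by a method that cannot deliver one, although a better method is already in use for efficacy.

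**Conclusion.** The point holds as a mismatch between aim and method in the readable text, not as a stated false conclusion. Under the assumed 20% Reference rate, a true 10-point excess on Test would go unflagged in about 69% of trials at 100 per arm and 53% at 150. A non-significant result could sit beside a 95% upper limit of about +26 or +20 points. Larger arms shrink these figures, and excesses of 20 points are mostly detected. Adverse event profiles and site reactions are also compared descriptively, so the p-value would not stand alone, and the primary efficacy conclusion is unaffected. The change is worth making before the blind is broken. Confidence is medium because of the redaction in Protocol 2.2 and the unreadable sample size.

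**What to change.** 1. In Protocol 8.1.5 and SAP 5.6, report the Test-minus-Reference difference in the proportion of ITT subjects with any TEAE, with a two-sided 95% confidence interval. Wald-Yates is consistent with the efficacy method; use Newcombe or Miettinen-Nurminen if events are sparse. Present it as an estimate, not a pass/fail rule.
2. Keep Fisher's test as supplementary, and state that a non-significant result is not evidence of comparability.
3. As no safety margin is readable, describe the safety comparison as descriptive and replace the word equivalence in the synopsis.
4. In the comparison sentences of Protocol 2.2 and 8.1.5 only, name TEAE as the tested set, as the SAP does. Leave the recording of adverse events from consent unchanged.
5. Optional and separate: add a table by arm of each subject's worst post-baseline grade for the six application site reactions, since SAP 5.6 summarizes them by visit.

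The cost is wording and a small amount of output from data already collected. The downside is that the interval may prove too wide to support a firm statement about comparable safety.
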